## **Methodology**

### **Research Design**

Research Design for EFFECTIVENESS TRIAL:

The research design for the EFFECTIVENESS TRIAL will include a randomized trial (N=250) comparing participants assigned to the Living Well self-management intervention or the medical illness education and support comparison group. Using an intent-to-treat framework, we will collect data from every participant at four time points, at consent, at randomization, post-treatment (3 months from randomization assessment), and again 3 months later (6 months from randomization). Services data regarding use of the ER and other medical services including outpatient appointments with primary and

specialty care medical providers within the VA will be collected at the follow-up assessment (6 months from randomization) as this allows for a more realistic timeframe for assessing effects on service utilization. To inform related analyses we will also collect retrospective service utilization data for a full six months before consent. We will recruit participants from outpatient programs with the VAMHCS (Baltimore and Perry Point) and from the DCVA.

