#### **Procedures defining the consent, randomization, post-treatment and 6 month follow-up Veteran assessments:**

All participants will complete assessment interviews at the time of consent, randomization post-intervention (3 month post-randomization), and 3 months post treatment (6 months from randomization). Trained RAs blind to the participant's condition assignment will administer all assessments. In order to ensure that the assessors remain blind, the RA completing the randomization interview (who then informs the participant of their treatment condition) will not complete the post-treatment or 3-month post-treatment follow-up interview with that same participant. However, the post-treatment and 3-month post-treatment follow-up interview may be completed by the same RA. Prior to starting the post-treatment and 3-month post-treatment follow-up, participants will be told not to reveal their study condition (Living Well or medical illness education and support group). If they do, the RA will make a note in the interview materials indicating that the blind was compromised and at what point during the interview this occurred. This RA will still complete the rest of the interview with the participant. If the blind does become compromised, a different RA will conduct the next scheduled assessment. Interviews will take approximately 1 ½ to 2 hours to complete. Please see Detailed Description of Measures section of this protocol for list of assessments and interviews included in the follow-ups.

If study staff is unable to contact enrolled participants by telephone to schedule a randomization, post-intervention, or 3 month post-treatment interview, a letter will be sent to participants to let them know we are attempting to contact them.

Also, we will include CPRS/Chart Summaries of Medical ER Use and Prescribed Medications: CPRS extracted chart data (including admission and discharge codes) will be extracted and used to summarize rates, patterns and reason for visit for the six month interval post randomization. The decision to look at this for a full six months in lieu of immediately post-treatment was made in order to allow for a more realistic timeframe for assessing intervention effects on service utilization. We will also extract details regarding both psychiatric and somatic medications.

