#### Data Analysis

##### FOR EFFECTIVENESS TRIAL:

Primary Hypotheses (regarding functional and service-related outcomes):

Hypothesis 1 (H1): Compared to those receiving a general medical illness education and support group, participants receiving Living Well will demonstrate greater improved general health functioning including both physical and emotional functioning.

To test the null hypothesis of no difference in improved general health functioning, we will use a longitudinal mixed effects model to compare change in mean physical and emotional health functioning from randomization to post-treatment. Regression equation (random effects not presented) at each time point will be:

SF12 function = Intercept + site + covariates + study condition + time + study-condition\*time + error

Notes: (1) Test of the null hypothesis of no difference in change from randomization to the post-treatment assessment will be conducted using a specified contrast. (2) "Study condition" is a dichotomous variable indicating study condition; (3) A random intercept and random slope (coefficient for time) will also be specified for the model; (4) The "time" variable will be entered as a continuous variable with possible values 0, 3, and 6 corresponding to the three assessment points (randomization, post-treatment, & 3-month follow-up); (5) The "covariates" terms represent adjustment for age, race, gender, and important potential confounders and will include Charlson comorbidity index score, chronic somatic illness

category, and any other covariate found to significantly differ at randomization (provided no significant collinearities are found). We are expecting few chance differences at randomization due to large sample size and random study condition assignment; (6) We have included a “site” term to adjust for site differences.

Hypothesis 2 (H2): Compared to the medical illness education and support group, the Living Well group will have a lower proportion of participants who will have had an emergency room visit for management of a chronic medical condition during the six months after randomization.

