For proportion with ER use in the past 6 months, we will use a random intercept mixed effects model since this outcome is assessed at only 2 time points. We will use a model that assumes no difference at randomization given the large sample size and randomization to study condition. Thus we will not include study condition as a main effect which would correspond to an assumption of unequal randomization rate of ER use. Some chance variation is expected and we will test the assumption of equal randomization rates with a chi-square test comparing the ER use rates by study condition. This model is equivalent to adjusting for randomization in the continuous case and we are taking this approach to be able to have .80 power to detect a smaller percentage point difference in ER use (50) at the 3 month follow-up assessment than if we didn’t assume equal rates at randomization. In the very unlikely scenario of a statistical difference at randomization we will add the study condition main effect to the model below, and the test of the null for H2 will continue to be the test that the coefficient for the study-condition-by-time interaction term is zero. To compare the two conditions on probability (p) of an ER visit, we let the outcome variable  $Y = 1$  if the participant had an ER visit in the prior 6 months (at randomization or at 3-month follow-up) and  $Y = 0$  if participant did not have an ER visit. Analysis model (logistic mixed effects model, random intercept not displayed) will be:

$$\text{logit}(E[Y]) = \text{Intercept} + \text{site} + \text{covariates} + \text{time} + \text{study-condition} \cdot \text{time}$$

where  $E[Y] = p = \text{probability participant has an ER visit in the prior six months at either randomization or 3 month follow-up (depending on “time” variable)}$ .

Notes: (1) Test of H2 will be the F-test that the coefficient for the study condition-by-time interaction is zero; (2) Study condition indicator main effect is omitted based on assumption of equal rates at randomization as discussed above; (3) For this hypothesis, “time” is a binary variable indicating assessment at 3 months post-treatment versus assessment at randomization; (4) The “covariates” terms represent adjustment for age, race, gender, Charlson comorbidity index score, chronic somatic illness category and other potential confounders found to be significantly different at randomization, (5) We have included a “site” term to adjust for site differences.

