In exploratory analyses we will categorize evident causes for emergency room admission and describe and compare the distribution of causes across the 5 chronic medical condition categories using a two-way table with row percentages. Associations between chronic medical condition and cause of emergency room admission will aid us in interpreting results for our ER primary outcome.

Secondary Hypotheses (3 and 4 - regarding more proximal attitudinal and behavioral outcomes):

Hypothesis 3 (H3): Compared to those receiving a general medical illness education and support group, participants receiving Living Well will report improved health-related self-efficacy and patient activation. Further, such improvements will mediate the effects on functional outcomes and ER use.

For self-efficacy and patient activation as outcomes, we will use a parallel model as for Hypothesis 1 to Version 9, 5/1/2015

compare the two study conditions. To test whether change in health-related self-efficacy or patient activation mediates the effect of Living Well we will estimate the mediated effect with a 95% confidence interval. When there is a mediating variable (i.e. mediator), the total effect of treatment can be divided into two components: (1) the direct effect of treatment (independent of the mediator), and (2) the mediated effect (i.e. indirect effect of treatment through the mediator (50). To estimate the mediated effect we will first estimate the total effect of Living Well and second, the direct effect of Living Well, and then estimate the mediated effect by subtracting the second from first. The estimate of the total effect of Living Well will be the treatment effect from the primary analysis model under either H1 or H2. The estimate of the direct effect of Living Well will be the treatment effect of Living Well after adjusting for the mediator. The mediator will be the change score of health-related self-efficacy or patient activation from randomization to post-treatment (for the functional outcomes) or randomization to the 3 month follow-up (for ER use). For statistical inference we will produce a 95% confidence interval around the mediated effect with a bootstrap procedure (51). We will interpret such a 95% confidence interval excluding zero as a statistically significant mediated effect.

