Hypothesis 4 (H4): Compared to those receiving a general medical illness education and support group, participants receiving Living Well will report improved self-management behaviors. Further, such improvements will mediate the effects of the functional and service outcomes specified above.

We will use a parallel model as for Hypothesis 1 to compare the two conditions on the self-management behavior scales at post-treatment. The tests of mediation will be directly parallel to those described for the test of mediation in Hypothesis 3 for the functional and ER use outcome variables.

Secondary Hypothesis 5: Living Well participants will sustain improvements across functional, attitudinal and behavioral outcomes at follow-up (3 months post-treatment).

We will test sustained improvement by testing the null hypothesis of no difference in change from randomization to the 3-month follow-up assessment (2-sided test) which will be the test that the coefficient for the study condition-by-time interaction term in the primary model (see H1) is zero. This hypothesis applies only to outcomes obtained from interview, not for ER visit and other 6-month service utilization variables. All available data will be included in these intent-to-treat analyses. The aforementioned analysis plan regarding dropout will be used.

Exploratory analyses: We will conduct several exploratory analyses.

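### The ER mediation tests in H3 and H4 measure the mediator at month 6, after every ER visit counted in months 0-6, so an interval excluding zero does not by itself show mediation

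*Protocol*

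**What the plan says.** All references are to the Protocol.

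- **Mediator.** Data Analysis, Hypothesis 3, defines the mediator as the change in self-efficacy or patient activation "from randomization to post-treatment (for the functional outcomes) or randomization to the 3 month follow-up (for ER use").
- **Visit timing.** Research Design places the assessments at "post-treatment (3 months from randomization assessment), and again 3 months later (6 months from randomization"). The 3-month follow-up is therefore month 6.
- **Outcome.** Hypothesis 2 concerns an "emergency room visit for management of a chronic medical condition during the six months after randomization". In the model, the outcome is 1 if the participant "had an ER visit in the prior 6 months (at randomization or at 3-month follow-up"). Study Procedures has chart data used to "summarize rates, patterns and reason for visit for the six month interval post randomization".
- **Estimator.** Hypothesis 3 estimates the total effect and the mediator-adjusted direct effect, and will "then estimate the mediated effect by subtracting the second from first", with a bootstrap interval.
- **Decision rule.** "We will interpret such a 95% confidence interval excluding zero as a statistically significant mediated effect".
- **Reach.** Hypothesis 4 (self-management behaviors) adopts the same procedure: "The tests of mediation will be directly parallel to those described for the test of mediation in Hypothesis 3".

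**The concern.** A mediator has to change before the outcome it is said to explain. Here the second mediator measurement is taken when the ER window closes, so every counted visit has already happened. A difference between total and direct effect could mean that the mediator prevented visits. It could equally mean that a visit altered the participant's self-efficacy, activation or self-management. The analysis cannot tell the two apart, yet the decision rule names only the first.

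The protocol gives a reason for the six-month ER window (a realistic period for utilization). It gives none for the mediator's timing, and it neither adds a safeguard for time order nor limits the interpretation. What is at stake is the claim in H3 and H4 that these attitudes and behaviors carry the ER effect.

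**Working it through.** **1. Time order**

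| Quantity | Months after randomization |
|---|---|
| Mediator, first measurement | 0 |
| Mediator also measured (post-treatment) | 3 |
| ER visits counted | 0 to 6 |
| Mediator, second measurement used for ER | 6 |

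No counted visit falls after the second measurement. This needs no assumption.

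**2. The protocol's own ER figure.** It states no figure for the mediation analysis, but the ER rates used below come from its sample size. With 25% against 10.7%, a difference of 0.143, mean 0.1785, two-sided 0.05 and power 0.80:

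- n = [1.960·√(2·0.1785·0.8215) + 0.842·√(0.1875 + 0.0956)]² / 0.143² = 111.4 per arm.
- With continuity correction: (111.4/4)·[1 + √(1 + 4/(111.4·0.143))]² = 125.0 per arm.

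The stated 125 per arm (250 in total) is reproduced with the continuity correction.

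**3. Size of the spurious effect.** Suppose the mediator has no effect on ER use, treatment raises it by a SD, and a visit lowers its month-6 value by d SD: M = a·arm - d·Y + standard normal error. Neither a nor d is in the documents. Then

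logit P(Y=1 | arm, M) = logit P(Y=1 | arm) - d·M + a·d·arm - d²/2.

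The direct effect is the total plus a·d, so total minus direct = -a·d. The total is ln(0.107/0.893) - ln(0.25/0.75) = -1.02.

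| a | d | Total minus direct |
|---|---|---|
| 0.5 | 0.5 | -0.25 |
| 0.4 | 0.5 | -0.20 |
| 0.4 | 0.25 | -0.10 |
| 0.3 | 0.25 | -0.075 |
| 0.4 | 0.1 | -0.04 |
| 0.5 | -0.25 (visit raises mediator) | +0.125 |
| 0 | 0.5 | 0 |
| 0.5 | 0 | 0 |

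Large simulated samples agree to within 0.01.

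**4. How often the interval excludes zero.** Each trial was simulated with no true mediation and a percentile bootstrap.

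- Follow-up logistic model, n = 250 / 220: a = d = 0.5, 79% / 69%; a = 0.3, d = 0.25, 14% / 15%; d = 0, 3% to 6%. Repeat runs with fewer trials gave 82% / 72% in the first case and 17% to 19% at n = 220 in the second.
- a = 0.4, d = 0.1, n = 220: about 8%.
- Two-time-point pooled logistic model: 12% to 80% if the mediator enters with time, 7% to 52% if it enters as a main effect.
- Visit raises the mediator by 0.25 SD, a = 0.5: 34% / 32%, all on the positive side, which would hide real mediation.

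**5. Which change restores time order.** n = 250 less 12% missing mediators, a = 0.4, equal visit risk in months 0-3 and 3-6, 400 trials per cell (Monte Carlo standard error up to 2.5 points). Share of intervals excluding zero:

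| d | As planned | Month-3 mediator, visits 0-6 | Month-3 mediator, visits 3-6 |
|---|---|---|---|
| 0.2 | 14% | 6% | 4% |
| 0.3 | 33% | 10% | 7% |
| 0.5 | 54% | 21% | 6% |
| 0.8 | 74% | 40% | 4% |

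**6. Price of the months 3-6 window.** With a constant visit rate, the three-month risks are 1 - √0.75 = 13.4% and 1 - √0.893 = 5.5%. Participants with an event: 125·(0.134 + 0.055) = 23.6, against 125·(0.25 + 0.107) = 44.6. Power for the total effect at two-sided 0.05:

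| Per arm | Uncorrected | Continuity-corrected |
|---|---|---|
| 125 | 0.57 | 0.48 |
| 110 | 0.52 | 0.42 |

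For months 0-6 at 125 per arm the same formulas give 0.84 and 0.80.

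**The case against.** The timing is plain in the text. The case on the other side concerns consequence and remedy.

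- **The harm rests on an unknown.** False mediation needs treatment to move the mediator, which H3 and H4 predict, and also a visit to shift it in a way that lasts to month 6. The documents give neither size nor sign for the second. This stands: the upper rates are a corner of an assumed grid. A reader might infer that the plan will probably declare mediation falsely. The documents do not support that.
- **The rates do not come from the planned model.** That model has a random intercept, site and covariates. The exclusion rates come from simpler models without them, and where the mediator enters matters a good deal. This stands, and the rates are illustrative. A large-sample check with a random intercept (person-level SD 1) still showed bias: -0.13 (main effect) or -0.28 (with time) of -1.14 at 0.5/0.5 SD, and -0.04 or -0.09 of -1.22 at 0.3/0.25 SD.
- **The functional outcomes are no better model.** A reader might take their month-3 mediator as the sound pattern that the ER analysis missed. But the SF-12 outcome is the change to that same visit, so time order is not established there either.
- **Month 6 may have a purpose.** Living Well has monthly boosters for three months after post-treatment, and a month-3 mediator misses change in that period. The protocol does not give this as its reason, but the loss is real and belongs among the costs.
- **The months 3-6 analysis asks a narrower question than H2.** This also stands. It is a reason to state the limits of that analysis, but it does not make the month 0-6 interval evidence of mediation.

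**Conclusion.** The point holds as a defect of time order and interpretation. For ER use, the month-6 mediator follows every counted visit, so an interval excluding zero does not by itself justify the conclusion the protocol attaches to it. That part rests on the text alone.

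The size rests on assumptions. For treatment shifts of +0.3 to +0.5 SD and visit shifts of -0.25 to -0.5 SD, the spurious log-odds effect is about -0.07 to -0.25 of -1.02. The interval then excludes zero in roughly 15% to 80% of trials, or 7% to 52% with the mediator as a main effect in a two-time-point model. The rate is near nominal for a visit effect of 0.1 SD or less. The bias is zero if treatment does not move the mediator, and it changes sign if visits raise it.

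A reader might also infer that the ER result itself is compromised. It is not: H1, H2, the sample size and the between-arm comparisons in H3 and H4 do not use this mediator.

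**What to change.** In Data Analysis, Hypotheses 3 and 4:

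1. Stop reading the month 0-6 ER mediation interval as evidence of mediation, and report that analysis as associational.
2. Base any ER mediation claim on a time-ordered analysis: mediator change from randomization to post-treatment (month 3); chart-dated ER visits after post-treatment (months 3-6); adjustment for ER use before randomization; total effect re-estimated on the same outcome and sample.
3. Do not move only the mediator. With the month 0-6 window kept, early visits still precede it.

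No new assessment is needed. The month-3 interview and the chart extraction are already planned, and visit dates must be kept. The work is a reworded paragraph and modest programming.

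The protocol should state the downsides:

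- About 24 instead of 45 participants with an event (constant visit rate assumed), hence wider intervals and the lower power shown above.
- A narrower outcome than H2, which omits visits during treatment.
- Mediator change during the booster period is not captured.
- Small residual bias if early visits affect the month-3 mediator and the same people return. At 0.5/0.5 SD it was -0.11 of -8.4 percentage points in simulation with person-level SD 1, and about -0.3 to -0.5 points with SD 2 to 3.

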One, in the Living Well group we will utilize data collected at consent to examine outcome trajectories and change in trajectories in the transition from the pre-intervention period (2 months on average) to the intervention period (randomization to post-tx; 3 months) and the post-intervention period (post-tx to follow-up; 3 months). For this analysis, time will be treated as continuous as time from consent to randomization will vary. A spline will be used starting at randomization to detect change in slope when the intervention commences. This analysis will allow comparison of the Living Well group to themselves prior to intervention. Two, we will examine whether improvements on primary and secondary outcomes in the Living Well condition relative to the control condition differ among 5 chronic medical condition subgroups: a) diabetes; b) a respiratory illnesses (including asthma and COPD); c) arthritis, d) a cardiovascular condition (e.g. congestive heart failure); or e) two or more of (a) thru (d). We will describe treatment effects by chronic illness sub-group, computing average treatment effect for each subgroup. We will also add the 3-way interaction term between study condition, time, and chronic illness category to the primary analysis models in order to perform a global test of differential improvement on outcomes by

chronic medical condition subgroup.

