Two, we will examine potential covariate moderators of treatment effect (e.g. participant demographic and clinical characteristics-see list of measures above) on the effectiveness of the intervention. To do this we will utilize the primary models but add the 3-way interaction term between the participant characteristic of interest, study condition indicator and time and through a contrast, test the null hypothesis of no relationship between the covariate and improvement on study outcomes. Three, we will examine effects on additional medical services utilization outcomes (e.g. somatic inpatient hospitalization, outpatient visits) as well as on medication adherence. Models parallel to H2 (ER use) will be used to examine treatment effects on these secondary outcomes. Four, we will examine whether treatment effects differed by site. For these analyses we will include the 3-way interaction term between study condition, time, and site to test overall interaction with an omnibus F-test. If the F-test is significant we will report treatment effects by site, and assess site differences in participant characteristics and otherwise investigate and summarize site characteristics that might explain differences. Five, we will examine how “dose” of intervention (i.e. number of sessions attended) and participation ratings (measured using the Group Performance measure described in the measures section) relate to study outcomes. Separately, in both the Living Well and the control condition we will use regression models to examine whether the covariate (either number of sessions attended or the Group Performance measure) is associated with improvement on outcomes. Models for these analyses (whether outcome is assessed at all 3 time points or just at randomization and 3 mo f/u) will include time and the dose-by-time interaction term to assess the relationship between dose and trajectory over time. For ER use and other dichotomous service utilization outcomes this analysis will assess change in proportion with ER in relation to dose. Six, we will similarly examine how fidelity ratings of adherence and competence relate to the functional, attitudinal, behavioral, and service related outcomes specified. In models similar to those used above to examine dose response relationships we will examine the relationship between overall adherence (and competence) and change in outcomes separately for each condition.

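### The exploratory moderator analysis states a null about predicting improvement, not about whether the Living Well effect varies with the covariate, and leaves the lower-order terms unnamed

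*Protocol*

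**What the plan says.** The passage is in the protocol, Data Analysis, FOR EFFECTIVENESS TRIAL, among the exploratory analyses. It is the second of two items that are both numbered two.

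- **Aim:** "we will examine potential covariate moderators of treatment effect".
- **Model:** take the primary models and "add the 3-way interaction term between the participant characteristic of interest, study condition indicator and time".
- **Null, tested through a contrast:** "test the null hypothesis of no relationship between the covariate and improvement on study outcomes".

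The H1 model being extended begins "SF12 function = Intercept + site + covariates + study condition + time" and ends with the condition-by-time term. It has no covariate-by-time and no covariate-by-condition term. Condition "is a dichotomous variable indicating study condition", with no numeric coding given, and time is "entered as a continuous variable with possible values 0, 3, and 6". In the H2 (ER) model the "Study condition indicator main effect is omitted based on assumption of equal rates at randomization".

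Two neighbouring analyses use the same device. For chronic illness groups the plan is to "add the 3-way interaction term between study condition, time, and chronic illness category to the primary analysis models", as a global test of whether improvement differs by group. For site, a three-way term is tested with an omnibus F-test of interaction.

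**The concern.** A moderator is a characteristic across which the difference between conditions varies. The stated null says nothing about conditions. It is false for any characteristic that goes with greater or smaller improvement, even when Living Well and the control group differ by the same amount at every level of it. An analyst who builds a contrast for that null tests prognosis and reports it as moderation.

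The model description does not guard against this. If the three-way term is the only addition, and condition is coded 0/1, that term is the only place where the covariate can relate to change, so it absorbs prognosis as well. The candidate moderators are demographic and clinical characteristics from a long list of measures, and some of these may well predict change. The practical risk is a misleading statement about whom the programme suits.

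**Working it through.** The protocol gives no power, sample size or error rate for the moderator analysis, so there is no figure to reproduce. The check asks how often each reading of the text declares a moderator when there is none.

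**Inputs from the protocol.** Sample Size, SF-12 paragraph: 110 per arm after attrition, correlation .50 between repeated measures, two-sided .05, effect size .40. H1 notes: times 0, 3 and 6.

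**Assumptions not in the protocol.** Standard-normal covariate X with a main effect of 0.3 SD; outcome SD 1; random intercept only, covariance treated as known; condition coded 0/1 unless noted; 2,000 simulated trials per setting.

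**Step 1: what each null refers to.** Let A be condition and t be time scaled so that the last visit is 1. The hierarchical model is

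E[Y] = b0 + b1·X + b2·A + b3·t + b4·X·A + δ·X·t + θ·A·t + γ·X·A·t.

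Change by the last visit is b3 + θ·A + δ·X + γ·X·A. The treatment effect on change at a given X is θ + γ·X, so the moderation null is γ = 0. The relation of X to improvement is δ in the arm coded 0 and δ + γ in the arm coded 1, averaging δ + γ/2. With γ = 0 and δ ≠ 0 there is no moderation, yet the stated null is false.

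**Step 2: size for the null as worded, by hand.** With t = 0, 0.5, 1 the centred sum of squares is 0.25 + 0 + 0.25 = 0.5. The per-person slope variance is (1 − 0.50)/0.5 = 1. The standard error of δ + γ/2 with 220 participants is 1/√220 = 0.0674. For δ = 0.1, 0.2, 0.3, 0.4 and γ = 0, z = δ/0.0674 = 1.48, 2.97, 4.45, 5.93. Rejection is about Φ(z − 1.96) = .32, .84, .99, 1.00. The simulation below agrees.

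**Step 3: three-way term without X·t.** Under 0/1 coding X·A·t is non-zero only in the arm coded 1, so it picks up δ there. In the simulation its mean was 0.08, 0.17, 0.26 and 0.34 for δ = 0.1 to 0.4, although true γ was 0.

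Share of trials declaring a moderator, true moderation zero, times 0/3/6:

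| Common X-by-time effect δ (SD) | 0 | 0.1 | 0.2 | 0.3 | 0.4 |
|---|---|---|---|---|---|
| Null as worded (arm-averaged relation) | .05 | .31 | .83 | .99 | 1.00 |
| Three-way term, no X·t, 0/1 coding | .05 | .15 | .48 | .82 | .96 |
| Three-way term, no X·t, −1/+1 coding | .05 | .05 | .06 | .07 | .07 |
| Hierarchical model, test of γ | .05 | .05 | .06 | .05 | .05 |

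With only times 0 and 3, the second row becomes .05, .15, .51, .80, .97.

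**Step 4: masking.** With δ = 0.2 and true γ = −0.2, the relation in the arm coded 1 is 0.2 − 0.2 = 0. The three-way-only model (0/1) then rejected in 6% of trials, against 31% for the hierarchical test. By hand, the standard error of γ is √(2/110) = 0.135, so z = 0.2/0.135 = 1.48 and power is about .32. Real moderation can therefore also be missed.

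**The case against.** The best defence is that the sentence is compressed rather than mistaken. It opens with moderators of treatment effect. The illness and site paragraphs around it ask plainly whether the treatment effect differs. The dose and fidelity analyses, which do concern association with change, have their own models, run within each condition. The authors evidently know the difference. Naming the highest-order interaction is common shorthand for a model with all lower-order terms, and a full list of terms is something a statistical analysis plan may supply.

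Much of this stands. A reader might infer that the three-way term is the only one added. The protocol neither says so nor excludes the lower-order terms, and the 0/1 coding behind the 15% to 96% is also an assumption. A reader might also infer that any prognostic covariate would be declared a moderator. The rates depend on how strong the relation is, and with −1/+1 coding they stay at 5% to 7%. Nor do the illness-category and site analyses share the misworded null, since their targets are stated correctly. The missing condition main effect in H2 is a deliberate equal-baseline choice and is not a source of this problem.

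The defence does not remove the null itself. It is written out, it is the hypothesis the contrast is to test, and it is the wrong one for the stated aim. That is a misstatement, not detail left for later.

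**Conclusion.** The concern holds as a fault in one stated null, together with an unstated model hierarchy. If the null is tested as worded, a purely prognostic covariate is called a moderator in about 31% to 100% of trials at common effects of 0.1 to 0.4 SD. If the three-way term is fitted with a 0/1 indicator and no covariate-by-time term, the range is about 15% to 96%. The hierarchical test holds about 5%. These figures rest on the assumed covariate distribution, main effect and random-intercept structure. The second range also rests on a reading the protocol permits but does not state.

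The consequence is limited. The analyses are labelled exploratory, and the tests of the primary and secondary hypotheses do not use them. A reader might infer that moderator findings will shape the implementation toolkit. The protocol says only that trial outcome data will feed into it and does not mention moderator or subgroup results. This is a minor point, worth correcting because the correction is so small.

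**What to change.** In the moderator paragraph, replace the null with: the condition-by-time effect does not vary with the covariate, tested by the covariate-by-condition-by-time coefficient.

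Then name the other terms:

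- **H1-type models:** covariate-by-time and covariate-by-condition, plus the covariate's main effect where it is not already an adjustment covariate.
- **H2-type models:** the covariate's main effect on the same basis, and covariate-by-time. Covariate-by-condition should follow the equal-baseline assumption: left out while the condition main effect is left out, and added if the protocol's own fallback brings that main effect back.
- **Illness category and site:** keep the stated targets and confirm that the same lower-order terms are included.

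This costs a sentence or two, with no new data and no change to sample size or to the confirmatory analyses. The hierarchical test has modest power (about 31% for moderation of 0.2 SD per SD of the covariate under the assumptions above), so a non-significant result should not be read as showing a uniform effect.
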